7.3.7 Visit 08, Day 14 (Window: +/- 3 days)

- Targeted physical exam performed, if indicated.
- Assessment of any side effects or adverse events.
- Any subject with worsening diarrhea as assessed by the study physician, may have their dose discontinued and receive standard of care metronidazole.
- Medical history, including any concomitant medications, reviewed.

- Stool sample will be collected for ova and parasite testing. The window for stool specimens will be +/- 3 days from the visit date and the date of collection noted.

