APPENDIX A: SCHEDULE OF EVENTS

Procedure	Visit* Number	00A	00B	01	02	03	04	05	06 ²	07	08	09	10 ²
	Study Day	-4	-4	1	2	3	4	5	6	7	14	28	30
	Window (days)	-4 to1	-4 to -1	+1 ⁶ ---	---	--+1-	---	+1 ⁶ ---	---	+1	+/-3	+/-3	+/-3
Review Eligibility		X		X									
Informed Consent		X											
Demographic Data		X											
Medical History			X	X	X	X	X	X	X	X	X	X	
Targeted Physical Exam ³			X	X	X	X	X	X	X	X	X	X	
Vital signs ⁴			X	X									
Concomitant Medications			X	X	X	X	X	X	X	X	X	X	
Randomization/ Enrollment				X									
Assessment for side effects of treatment					X	X	X	X	X	X	X	X	
AEs/SAEs				X	X	X	X	X	X	X	X	X	
Urine for pregnancy testing			X										
Treatment (giardiasis subjects)				X	X	X	X	X					

Treatment (E. histolytica)				X	X	X	X	X	X	X			
Procedure	Visit Number	00A	00B	01	02	03	04	05	06 ³	07	08	09	10 ⁴
	Study Day	-4	-3	1	2	3	4	5	6	7	14	28	30
	Window (days)	-4 to 1	-3 to -1	+1 ⁸ ---	---	--+1 ⁸ -	---	+1 ⁸ ---	---	+1	+/-3	+/-3	+/-3
Urine Dipstick for Proteinuria			X							X			
Complete Blood Count ⁵			X							X			
BUN			X							X			
Creatinine			X							X			
ALT			X							X			
AST			X							X			
Stool specimen ⁶		X		X		X		X		X	X	X	
Blood volume			17							17			
Blood volume totals			17							34			
Standard of Care Treatment													X

*Subjects will be enrolled at the icddr,b or Rajshahi Hospitals and have follow-up visits until their diarrhea has resolved. Subsequent follow-up visits may be held at the icddr,b or Rajshahi Hospital, or local (to Rajshahi) clinic or their home except for Visit 07 which must be performed at icddr,b or Rajshahi Hospital or Clinic because blood drawing is required.

¹Visit 06 will only be conducted for subjects receiving treatment for amebiasis.

²Visit 10 will only be conducted for subjects who remain positive for amebiasis or giardiasis at Day 28 and have not previously received standard of care treatment.

³Targeted physical exam may also include observations for rashes, hair loss, urticaria or glossitis, and an abdominal exam.

⁴Vital signs (oral temperature, pulse, blood pressure)

⁵Complete blood count includes white blood cells, hemoglobin, and platelet count.

⁶Window of + 1 day for stool specimens after (and including) Day 1. Date of collection will be noted. The window does not apply to treatment administration or other required assessments.

⁷Amebiasis patients only

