	SST (10 ml)	BUN, Cr, SGOT, SGPT,	Refer to Screening Visit 00B
Day 14, Visit 08 +/- 3 days	Stool collection vial for Full Stool Evaluation	Refer to Day 1 If positive at Day 14, perform parasite genotyping. (Not performed on patients who receive metronidazole prior to completing dosing regimen)	Refer to Day 1 Stored DNA sent to UVA for parasite genotyping every 1-3 months
Day 28, Visit 09 +/- 3 days	Stool collection vial for Full Stool Evaluation	Refer to Day 1 If positive at Day 14, perform parasite genotyping. (Not performed on patients who receive metronidazole prior to completing dosing regimen)	Refer to Day 1 Stored DNA sent to UVA for parasite genotyping every 1-3 months

**APPENDIX C: ICDDR,B NORMAL LABORATORY VALUES
(APPLICABLE FOR BOTH SITES)**

	Male	Female
White Blood cells ($10^9/L$)	4.0 – 11.0	same
Platelets ($10^9/L$)	150.0 – 450.0	same
Hemoglobin (gm/dL)	12.5 – 17.5	11.5 – 16.5
Blood urea nitrogen (mg/dL)	5 – 24	same
Creatinine (umol/L)	53-106	44-97
AST/SGOT (U/L)	0.01 – 38.0	0.01 – 32.0
ALT/SGPT (U/L)	0.01 – 41.0	0.01 – 31.0

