3.3. Study Definitions and Derived Variables

For the purposes of enrollment into the asymptomatic population, potential subjects are *diagnosed with amebiasis or giardiasis* if they have a positive TechLab antigen test, positive wet mount or trichrome, and positive stool PCR for *E. histolytica* or *Giardia*. In order to enroll, the subject must receive the diagnosis of amebiasis or giardiasis within 72 hours of enrollment. If a subject is infected with both *E. histolytica* and *Giardia*, they will be enrolled in the *E. histolytica* study arm. Once the *E. histolytica* study arm is fully enrolled, any subsequent dual infected subjects will be enrolled in the *Giardia* arm.

For enrollment into the symptomatic population, potential subjects are *diagnosed with amebiasis or giardiasis* if they have a positive rapid EIA and positive antigen detection EIA of *E. histolytica* or *Giardia*. These subjects must also have diarrhea (3 or more loose stools within 24 hours of enrollment). In order to enroll, the subject must receive the diagnosis of amebiasis or giardiasis within 4 days prior to enrollment. If a subject is infected with both *E. histolytica* and *Giardia*, they will be enrolled in the *E. histolytica* study arm. Once the *E. histolytica* study arm is fully enrolled, any subsequent dual infected subjects will be enrolled in the *Giardia* arm. If a subject is infected with both *Giardia* and *Cryptosporidium*, they will not be enrolled.

Parasitological response is defined as no detection of cysts or trophozoites on microscopic exam or negative antigen detection, for the asymptomatic population. Both tests will be performed on each subject. For the symptomatic population, however, **parasitological response** is defined as no detection of trophozoites on microscopic exam. The microscopic exam may include both wet mount and trichrome staining. If both were performed, then both must be negative for the microscopic exam to be negative.

Sustained cure on Day 14 is defined, for the asymptomatic amebiasis group, to be no detection of cysts or trophozoites on microscopic exam or negative antigen detection on Day 7 and again on Day 14. ***Sustained cure on Day 14*** is defined, for the symptomatic amebiasis group, to be no detection of trophozoites on microscopic exam on Day 7 and again on Day 14. ***Sustained cure on Day 14*** is defined analogously for the giardiasis groups but is based on measurements taken on Day 5 and 14.

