Sustained cure on Day 28 is defined for the asymptomatic amebiasis group to be no detection of cysts or trophozoites on microscopic exam or negative antigen detection on Days 7, 14, and 28 (if specimens are obtained at each time point). ***Sustained cure on Day 28*** is defined for the symptomatic amebiasis group to be no detection of trophozoites on microscopic exam on Days 7, 14, and 28 (if specimens are obtained at each time point). It is defined analogously for the giardiasis groups but is based on measurements taken on Day 5, 14, and 28.

Relapse at Day X is defined as having a positive stool PCR at day X that is identified via genotyping to be identical to the strain of the original infection.

Reinfection at Day X is defined as having a positive stool PCR at day X that is identified via genotyping to be non-identical to the strain of the original infection.

In the two above definitions, the ***original infection*** is defined to be the strain of parasite measured in the stool sample collected on Visit 01.

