6.5. Missing Data

The primary analysis involves comparison of a binary response between the treatment group and the placebo group. This is true for both asymptomatic and symptomatic populations, whose primary outcomes are parasitological response and resolution of diarrhea, respectively. Within each population, the response is measured at Day 7 for the amebiasis group and Day 5 for the giardiasis group. In the symptomatic population, subjects who terminate their treatment regimen and receive metronidazole due to worsening symptoms will be imputed as treatment failures for the primary outcome. That is, they will be imputed as still symptomatic by Day 7 in the amebiasis group, and by Day 5 in the giardiasis group. Secondary outcomes measured at Days 3, 5, and 7 will be imputed analogously, with the exception of the quantitative trophozoite/cyst load.

The rest of the text in this section applies to both asymptomatic and symptomatic populations.

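### The SAP's rescue-as-failure rule stops at Day 7, so negative stools after later metronidazole can count as sustained cure, and Day 14 antigen in rescued amebiasis subjects has no rule

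*SAP*

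**What the plan says.** SAP 6.5 (Missing Data) sets the rule for symptomatic participants as follows: "subjects who terminate their treatment regimen and receive metronidazole due to worsening symptoms will be imputed as treatment failures for the primary outcome". It extends the rule once: "Secondary outcomes measured at Days 3, 5, and 7 will be imputed analogously, with the exception of the quantitative trophozoite/cyst load". Protocol 11.4 has the same scope.

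The secondary outcomes run later than that. SAP 3.2.2 lists stool antigen through Day 14 for amebiasis (giardiasis stops at Day 5), and sustained cure and relapse or re-infection at Days 14 and 28 for both groups. SAP 3.3 defines Day 14 sustained cure "for the symptomatic amebiasis group, to be no detection of trophozoites on microscopic exam on Day 7 and again on Day 14". The Day 28 version is "no detection of trophozoites on microscopic exam on Days 7, 14, and 28". Giardiasis uses Day 5 in place of Day 7.

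Protocol 7.3.7 (Visit 08, Day 14) states: "Any subject with worsening diarrhea as assessed by the study physician, may have their dose discontinued and receive standard of care metronidazole". Visit 07 carries the same provision. Appendix A limits the Day 30 visit to subjects still positive at Day 28 who "have not previously received standard of care treatment", so treatment before then is foreseen. For the Day 14 and Day 28 stools, Appendix B carries the note "Not performed on patients who receive metronidazole prior to completing dosing regimen".

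**The concern.** The sponsor chose to count rescue as failure, but the rule ends while rescue is still allowed. It also depends on terminating the regimen, and a subject rescued after the last dose has terminated nothing. Sustained cure is meant to describe how long the response to auranofin or placebo lasts. If negative stools after metronidazole count towards it, the result in an arm is partly a metronidazole result and durability in that arm can be overstated. Relapse and re-infection are affected too, because SAP 3.3 requires a positive stool PCR and a stool cleared by metronidazole will not show one.

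**Working it through.** **1. Timing.** Giardiasis dosing ends on Day 5 and amebiasis dosing on Day 7. Visit 07 (Day 7) is therefore after dosing for giardiasis, and Visit 08 (Day 14) is after dosing for both groups.

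**2. Following subjects through the rules as written.**

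- *Giardiasis, negative on Day 5, metronidazole at Visit 07, negative on Days 14 and 28.* The regimen was completed, so the failure rule does not apply, and the Appendix B note does not stop testing. Scored a sustained cure at Day 14 and at Day 28.
- *Either group, negative through Day 14, metronidazole at Visit 08, negative on Day 28.* Scored a Day 28 sustained cure.
- *Either group, rescued before completing dosing.* The Day 5 (giardiasis) or Day 7 (amebiasis) result is imputed as failure. Sustained cure needs that day to be negative, so failure is inherited and there is no gap.
- *Amebiasis, rescued before completing dosing, Day 14 antigen.* The rule stops at Day 7. If Appendix B means no Day 14 testing, the value is missing and SAP 6.5 sends it to multiple imputation under missing at random, where rescue is not a listed predictor. If the note covers genotyping only, a negative result after metronidazole counts directly as clearance.

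The per-protocol set does not repair this. Subjects rescued after dosing meet its 80% dosing criterion (SAP 6.3.2), and the rescue itself is permitted by the protocol.

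**3. Size for sustained cure.** The plan states no figure to reproduce. With 34 per arm (SAP 5), one misclassified subject moves an arm by 1/34 = 2.9 points. Hypothetical counts, Fisher's exact test:

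- Under rescue-as-failure, 22/34 vs 12/34 gives p = 0.028. One placebo subject rescued late and counted as cured makes it 22/34 vs 13/34, p = 0.051.
- In the other direction, suppose rescue-as-failure gives 21/34 vs 12/34. This is the 22 vs 13 table with rows and columns exchanged, so p = 0.051. One auranofin subject rescued late and counted as cured makes it 22/34 vs 12/34, p = 0.028.

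**4. Size for Day 14 antigen (amebiasis).** All rates are assumed. Let q be the negative rate in subjects not rescued, r the share of the arm rescued early, and assume 80% test negative after metronidazole. An arm's negative proportion is then:

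- rescue as failure: q(1 − r)
- imputed with no rescue information in the model: q
- tested and counted: q(1 − r) + 0.8r

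Difference, auranofin minus placebo, in points:

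| q, aur/pbo | r, aur/pbo | Failure | Imputed | Tested |
|---|---|---|---|---|
| 80/20% | 0/10% | 62 | 60 | 54 |
| 80/20% | 5/20% | 60 | 60 | 48 |
| 80/20% | 10/30% | 58 | 60 | 42 |
| 80/20% | 10/10% | 54 | 60 | 54 |
| 70/30% | 0/10% | 43 | 40 | 35 |
| 70/30% | 10/10% | 36 | 40 | 36 |

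Third row: failure 0.80×0.90 − 0.20×0.70 = 0.72 − 0.14 = 0.58; tested (0.72 + 0.08) − (0.14 + 0.24) = 0.42.

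Moving from imputation to rescue-as-failure changes the contrast by +3 (40 to 43) to −6 (60 to 54) points. Moving from tested-and-counted to rescue-as-failure changes it by 0.8 × (placebo r − auranofin r), here 0 to +16 points.

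**The case against.** **The reach is narrow.** Visit 08 is where the Day 14 stool is collected, so metronidazole given there bears on Day 28 only, apart from a stool taken later in the ±3 day window. For amebiasis, late rescue can reach Day 14 outcomes only if metronidazole starts after the seventh dose at Visit 07, or between scheduled visits, and Protocol 7.5 on unscheduled visits does not mention it. This stands, and the point is confined accordingly.

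**Rescue-as-failure is a choice of estimand.** Sustained cure is a microscopy outcome, while rescue is triggered by worsening diarrhea with no requirement for a positive stool. Some rescued subjects may have been parasitologically cured. This stands and is why an as-observed analysis belongs beside the main one. But the sponsor already applies the rule to microscopy outcomes through Day 7, and no reason is given for ending it there.

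**The imputation may recover part of the information.** A reader might infer that Day 14 antigen is imputed as if rescue were random. The documents do not go that far: SAP 6.5 evaluates diarrhea, other symptoms and microscopy as predictors, and these can carry information about rescue. What stands is that rescue itself is not named. The written criterion, which admits covariates with p above 0.10, cannot be relied on to bring those variables in.

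**Missing Day 14 results are not established.** In the Day 14 row of Appendix B the note directly follows the genotyping instruction, and Protocol 5.3.4 encourages stool collection after withdrawal. Both readings leave antigen without a rule, but they lead to different errors.

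**Conclusion.** The gap is real and follows from the text. Two cases are clear: giardiasis subjects rescued at Visit 07 (sustained cure at Days 14 and 28) and subjects in either group rescued at Visit 08 (Day 28 only). Day 14 antigen after early rescue is a further gap, for amebiasis only, whose form depends on how Appendix B is read.

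A reader might infer that the trial is tilted towards auranofin, or that rescued subjects in general are scored as cured. Neither is supported. Subjects rescued before completing dosing already inherit failure for sustained cure. The documents give no rescue rates, so neither the size nor the direction of the effect on the contrast is known; the illustrations move it both ways. What can be said is that each misclassified subject is worth 2.9 points at 34 per arm. The primary outcome is not affected.

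**What to change.** Extend the sentence in SAP 6.5: a symptomatic subject who receives metronidazole for worsening symptoms before an assessment, whether or not dosing was complete, is a failure for Day 14 antigen (amebiasis) and for Day 14 and Day 28 sustained cure. The clause on completed dosing is essential, because adding the later days to the present sentence would still miss everyone rescued after the last dose.

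In the symptomatic versions of SAP Tables 31 to 34, do not impute these subjects as relapse or re-infection; show them in a separate category for receipt of metronidazole.

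The downside is that some subjects who may have been parasitologically cured become failures, so report sustained cure as observed as a sensitivity analysis.

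Two passages must also be reconciled: the Visit 08 text on discontinuing a dose after dosing has ended, and the scope of the Appendix B note at Days 14 and 28.

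The cost is one SAP sentence, a table category and one extra analysis. No new data are needed: concomitant medications are recorded to about Day 30 (Protocol 8.1), and SAP Listings 35 and 36 carry start day and indication. Protocol 11.4 gives the SAP precedence, so an SAP edit made before unblinding is enough for the analysis rule.

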However, the protocol endpoints and study population were revised because after screening 2,396 people during 17 months with only 34 enrolling into the study, it became apparent that enrolling 136 asymptomatic subjects would be infeasible. For this reason, eligibility criteria were revised, starting with protocol version 5, to enroll symptomatic rather than asymptomatic adult patients (still with amebiasis or giardiasis). The goal, as before, was to enroll 68 in each disease group and randomize in a 1:1 ratio within each disease group to receive either auranofin or placebo. The dosing regimen was unchanged, but the primary outcome was revised for the new (symptomatic) study population. The new primary outcome is resolution of diarrhea (less than 3 loose stools / 24 hours) by Day 7 for the symptomatic amebiasis group and by Day 5 for the symptomatic giardiasis group. Furthermore, in version 7 of the protocol, a new site was also added (Rajshahi Medical College Hospital), after which randomization was stratified by site as well as disease group. The protocol revision specified that the asymptomatic and symptomatic subjects would be analyzed separately.

The study populations, study design, and primary outcome for each of these populations are summarized by protocol version in [Table 1](#):

Table 1: Summary of Study Population, Study Design, and Primary Outcome by Protocol Version

Protocol Versions	Study Population	Target Sample Size	Treatment Allocation	Dosing Regimen	Primary Outcome
1-4	Asymptomatic amebiasis	68	1:1 (auranofin: placebo)	7 days	Parasitological response (no detection of cysts or trophozoites on microscopic exam or negative antigen detection) by Day 7
	Asymptomatic giardiasis	68	1:1 (auranofin: placebo)	5 days	Parasitological response (no detection of cysts or trophozoites on microscopic exam or negative antigen detection) by Day 5
5-7	Symptomatic amebiasis	68	1:1 (auranofin: placebo) ^a	7 days	Resolution of diarrhea (less than 3 loose stools / 24 hours) by Day 7
	Symptomatic giardiasis	68	1:1 (auranofin: placebo) ^a	5 days	Resolution of diarrhea (less than 3 loose stools / 24 hours) by Day 5

^a Randomization was also stratified by site for subjects enrolled under protocol version 7 because a second site was added in that protocol version.

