4.4.2. Method of Assigning Subjects to Treatment Groups (Randomization)

Per International Conference on Harmonisation (ICH) guideline E6: Good Clinical Practice (GCP), screening records will be kept at the icddr, b site to document the reason why an individual was screened, but failed trial entry criteria. The reasons why individuals failed screening will be recorded in the Statistical and Data Coordinating Center's (SDCC) Advantage eClinical Electronic Data Capture System.

In the asymptomatic population, eligible subjects were stratified by disease strata (amebiasis or giardiasis), and then within each stratum, randomized 1:1 to receive auranofin or placebo. Enrollment was to continue in the other stratum after one stratum reached full enrollment. All subjects were to receive doses of the assigned medication or placebo delivered orally on Days 1, 2, 3, 4, 5, 6, and 7 for amebiasis and Days 1, 2, 3, 4, and 5 for giardiasis.

For the symptomatic population, randomization is stratified by site to prevent confounding that could arise from imbalance in treatment allocations between sites. Because the relative pace of enrollment between the two sites is unknown, the number of participants to be enrolled at each site is not fixed in advance. With this approach, the faster enrolling site may enroll more subjects, allowing enrollment to complete as quickly as possible. Each site may enroll up to 68 subjects into each stratum, so it is possible that one stratum could be filled entirely with subjects from a single site. With this flexible approach, treatment assignments may not be perfectly balanced (overall or within each site), but they will be approximately balanced. With sample sizes of 68 in each stratum, the impact of a small imbalance on power is negligible. Once eligibility and consent are confirmed, symptomatic subjects are stratified by site and infection (amebiasis or giardiasis), and then within each stratum, randomized 1:1 to receive auranofin or placebo. Enrollment will continue in the other arm after one arm reaches full enrollment. All subjects receive the assigned medication or placebo delivered orally on Days 1, 2, 3, 4, 5, 6, and 7 for amebiasis and Days 1, 2, 3, 4, and 5 for giardiasis.

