The randomization codes were prepared by statisticians at the SDCC and included in the enrollment module for the trial. SDCC staff generated the randomization lists for each study population and site and sent corresponding documentation to the study sites. The randomization lists include the randomization codes to serially assign study treatment to subjects as they are assigned to the study (i.e., randomize subjects to study arm by study identification number). This table did not contain unblinded information; study staff were not able to see the study arm assignment for each study identification number.

Eligible study subjects were to be randomized under single-blind conditions by study staff members after consent. Since the placebo is similar but not identical to the study medication, only the lab personnel are truly blind, however the participants were not to be informed whether they receive study product or placebo. The randomization numbers were to be recorded on the study CRFs.

A designated individual at each site (icddr,b and Rajshahi Medical College hospital) was provided with the treatment key, which links the treatment code to the actual treatment assignment. This is kept in a secure place.

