6. GENERAL STATISTICAL CONSIDERATIONS

6.1. General Principles

Continuous variables will be summarized using the following descriptive statistics: n (non-missing sample size), mean, standard deviation, median, maximum and minimum. The frequency and percentages (based on the non-missing sample size) of observed levels will be reported for categorical measures. In general, all data will be listed, sorted by disease group, site, treatment and subject, and when appropriate by visit number within subject. In general, summary tables will be created separately for the four populations (asymptomatic amebiasis, asymptomatic giardiasis, symptomatic amebiasis, and symptomatic giardiasis), and will include columns for each treatment in the order (Auranofin, Placebo) and will be annotated with the total population size relevant to that table/treatment.

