In the primary analysis, no covariates are included, so the analysis involves two variables: the binary predictor (treatment/placebo) and the binary response (parasitological response: yes/no). Some subjects may have missing values for the response variable, for example, if they are unable to provide a stool specimen on the designated day. If all subjects are equally likely to have missing response values, then the data are Missing Completely At Random (MCAR), in which case these subjects may be dropped from analysis without biasing the results. If, on the other hand, missingness depends on other values which are observed, then the data are Missing At Random (MAR). It is possible that the data in this study will be MAR but not MCAR (which is a more stringent condition). For example, it is plausible that subjects in the auranofin group will be more likely to miss a stool specimen than those in the placebo group since constipation is one known possible side effect of auranofin. If this is the case, and if those who are missing response values in the auranofin group also experience a different response to treatment than those who remain in the study, then dropping these subjects from analysis will bias the estimate of the treatment effect. An appropriate approach to remove the bias from dropping these subjects from analysis is multiple imputation, which is proposed below. A third possibility for the missingness mechanism is that the missingness depends on one or more unobserved variables (and may depend on observed variables, as well). As all relevant symptom variables, as well as demographic variables, will be measured, it is unlikely that missingness pattern will depend on an unobserved variable. For the symptomatic population, microscopy results will also be evaluated as a predictor.

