14.1.2 Demographic Data by Study Group

Table 15: Distribution of Sex, Ethnicity, and Race by Treatment Group, Asymptomatic Population

This table will be repeated for the symptomatic population, but will also split out the summaries by site.

Demographic Category	Characteristic	Amebiasis Group, Auranofin, 6 mg (n=34)		Amebiasis Group, Placebo (n=34)		Amebiasis Group, All subjects (n=68)		Giardiasis Group, Auranofin, 6 mg (n=34)		Giardiasis Group, Placebo (n=34)		Giardiasis Group, All subjects (n=68)		All subjects (n=136)	
		n	%	n	%	n	%	n	%	n	%	n	%	n	%
Sex	Male	x	x.x												
	Female														
Ethnicity	Not Hispanic or Latino														
	Hispanic or Latino														
	Not Reported														
Race	Unknown														
	American Indian or Alaska Native														
	Asian														
	Native Hawaiian or Other Pacific Islander														
	Black or African American														
	White														
	Multi-Racial														
	Unknown														

Table 16: Age Statistics (in Years) by Disease Group and Treatment Group, Asymptomatic Population*This table will be repeated for the symptomatic population, but will also split out the summaries by site.*

Variable	Statistic	Amebiasis Group, Auranofin, 6 mg (n=34)	Amebiasis Group, Placebo (n=34)	Amebiasis Group, All subjects (n=68)	Giardiasis Group, Auranofin, 6 mg (n=34)	Giardiasis Group, Placebo (n=34)	Giardiasis Group, All subjects (n=68)	All subjects (n=136)
Age	Mean	X.X	X.X	X.X				
	Standard Deviation	X.X	X.X	X.X				
	Median	X.X	X.X	X.X				
	Minimum	X	X	X				
	Maximum	X	X	X				

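### Symptomatic randomization is stratified by site, but neither the SAP's primary comparison nor its secondary model uses site (minor; costs precision only if site predicts resolution)

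*SAP*

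**What the plan says.** SAP section 2 records that protocol version 7 added a second site, "after which randomization was stratified by site as well as disease group". SAP 4.4.2 gives the reason: "randomization is stratified by site to prevent confounding that could arise from imbalance in treatment allocations between sites". It adds that "SDCC staff generated the randomization lists for each study population and site". The same section concedes that "treatment assignments may not be perfectly balanced (overall or within each site), but they will be approximately balanced", and that "it is possible that one stratum could be filled entirely with subjects from a single site".

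On analysis, SAP 6.5 states for both populations: "In the primary analysis, no covariates are included, so the analysis involves two variables". Its analysis step computes a crude difference in proportions in each imputed data set. Tables 20 and 21, the symptomatic primary tables, show an unstratified difference, an odds ratio and a Fisher p-value.

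For the secondary logistic model, Protocol 11.4 lists stratification variables among the adjustment factors. The matching sentence in SAP 8.1.1 omits them and names demographics, vital signs and laboratory values as the baseline variables. Both documents admit a covariate only if it is associated with treatment and with outcome at p<0.10. Protocol 11.4 gives the SAP precedence where the two differ.

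Site is available to the analyst. SAP 6.1 says "all data will be listed, sorted by disease group, site, treatment and subject", and the notes to Tables 15 and 16 say "This table will be repeated for the symptomatic population, but will also split out the summaries by site".

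**The concern.** Two factors define the randomization strata. Infection is respected, because the disease groups are analyzed separately (SAP 6.4). Site is not. When allocation is balanced within site and site predicts the outcome, the crude standard error still counts between-site variation that the design has removed. Intervals are then too wide and the test too cautious.

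Giardiasis is where this could matter, because its stated power is 85%. Amebiasis has power to spare. The secondary model does not make up for the omission. Site is not on the SAP's list, and a screen requiring association with treatment works against a factor on which allocation was balanced.

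**Working it through.** **Inputs.** From SAP 5: two-sided alpha 0.05; giardiasis 70% vs 30%; amebiasis at least 80% vs 15-20%; 34 per arm; 60 of 68 completing, so 8/68 = 12% missing. The documents give no site effect and no site split. Both are assumed below, with overall rates held fixed and the same gap between sites in each arm.

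**The plan's own power.** Pooled normal formula for giardiasis, 30 per arm: z = [0.40 - 1.96√(2×0.25/30)] / √(0.42/30) = (0.400 - 0.253)/0.118 = 1.24, power 89.3%. At 34 per arm it is 92.8%. Fisher's test gives 83.8% at 30 and 87.6% at 34, so the stated 85% is reproduced to within about 2 points by Fisher at 30 completers. Amebiasis (80% vs 20%) is 99.8% by Fisher at 30, consistent with the stated figure of over 95%.

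**Why site matters.** With a fraction w of subjects at one site and a gap g between sites, the within-site variance in each arm is p(1-p) - w(1-w)g². For giardiasis p(1-p) = 0.21 in both arms.
- Equal sites, g = 0.20: 0.21 - 0.01 = 0.20; SE ratio √(0.20/0.21) = 0.976.
- Equal sites, g = 0.30: 0.21 - 0.0225 = 0.1875; ratio 0.945.
- Equal sites, g = 0.40: 0.21 - 0.04 = 0.17; ratio 0.900.
- 80/20 split, g = 0.30: 0.21 - 0.0144 = 0.1956; ratio 0.965.

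**With missing data and multiple imputation.** 40,000 simulated trials per scenario; 34 per arm; assumed missingness 6% at one site and 18% at the other; 20 imputations; small-sample t degrees of freedom. Giardiasis, equal sites, pooled risk difference:

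| Site gap | Power, unstratified | Power, by site | Half-width, unstratified | Half-width, by site |
|---|---|---|---|---|
| 0 | 89.2% | 88.7% | 23.4 | 23.7 |
| 20 | 89.6% | 90.1% | 23.4 | 23.1 |
| 30 | 90.1% | 91.8% | 23.4 | 22.4 |
| 40 | 91.3% | 94.6% | 23.5 | 21.4 |

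Gaps and half-widths are in percentage points. At an 80/20 split the power change is -0.5, 0.0 and +0.8 at gaps of 0, 20 and 30. Under the null, the unstratified analysis rejects in 5.3% of trials with no gap, falling to 3.3-3.7% at 40 points. The stratified analysis rejects in 4.8-5.2% throughout.

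**Complete data.** Giardiasis, equal sites, gaps 0/20/30/40, Fisher then continuity-corrected Cochran-Mantel-Haenszel (CMH):
- 30 per arm: 84.1/84.1, 84.2/84.6, 85.2/86.7, 86.3/90.3%.
- 34 per arm: 87.6/87.0, 87.8/89.5, 88.8/92.1, 89.6/94.4%.

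A separate exact enumeration over site odds ratios agrees. Fisher against an exact site-stratified test loses 0.2-1.7 points at a site odds ratio of 2, 0.8-2.8 at 3, 2.1-3.7 at 5 and 4.3-5.4 at 10. Fisher's type I error stays below 0.05, at 0.026-0.027 with no site effect and 0.013-0.019 at an odds ratio of 10. A mild chance imbalance (18/16 vs 16/18 by site) moves the crude giardiasis difference by 0.8 points at an odds ratio of 2 and 1.3 at 3. Amebiasis power changes by less than 0.1 point.

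**The p<0.10 screen.** Blocking is not stated. Under simple 1:1 allocation of 68 subjects at equal sites, site passes the treatment half in about 11% of draws. It passes both halves in 2.4, 6.0, 8.7 and 10.8% at gaps of 0, 20, 30 and 40. At a 90/10 split these are 2.0, 3.8, 5.5 and 6.5%. With blocks (assumed sizes 4 and 8) both halves pass in under 0.1% at 30 points. A split as uneven as 19/15 vs 15/19 still gives p = 0.33 for site against treatment. Site therefore stays out in at least 100 - 10.8 = 89% of trials.

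**The case against.** The primary analysis contains no error. Protocol 11.4 itself specifies an unstratified Fisher test, so on that point the SAP follows the protocol, and the test is valid. This stands, and it is why the point is minor.

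The gap between protocol and SAP is thin. The SAP's covariate list may not be exhaustive, residence location is collected as demographic data (Protocol 7.1.1), and silence need not revoke the protocol. But nothing in the SAP names site for the model. Restoring the missing words would not help either, since the protocol's screen is the same.

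Equal sites may be optimistic. Version 5 took effect on 12 December 2017 and version 7 on 23 July 2019, which is about 19 months of symptomatic enrollment at one site. Protocol 4 says the second site was added for amebic prevalence. An uneven giardiasis split is plausible, and the gain then shrinks toward zero. This also stands. So does the observation that the site gap, the imputation settings and the missingness by site are assumptions.

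Finally, the remedy replaces an exact test with an approximate one and costs a little when site has no effect. That is true, but the cost is about half a point of power.

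**Conclusion.** The concern holds and is minor. The plan stratifies by site and then analyzes as if it had not, and the SAP does not carry over the protocol's one provision for stratification variables. Type I error is not inflated. What is lost is precision: for giardiasis with equal sites, 0.5 points of power at a 20-point site gap, 1.7 at 30 and 3.3 at an extreme 40. With no site effect the unstratified analysis is 0.5 points better. The gain vanishes if one site fills the group. All of this depends on an assumed site effect, since the documents give none. Because the effect is unknown, the choice should be fixed before unblinding.

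**What to change.** For the symptomatic population only, amend SAP 6.5 and 8.1:

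1. In each imputed data set, compute the Mantel-Haenszel risk difference by site with a within-site (n-1) standard error. Pool it through the existing combination step, and take the primary p-value from the pooled estimate with the combination rules' t reference. If no response is missing, use a site-stratified exact or CMH test, and state which one, including any continuity correction. The exact test is the closer counterpart of Fisher's.
2. Always include site in the imputation model.
3. Force site into the secondary logistic model, outside the p<0.10 screen.
4. Before unblinding, require at least 5 subjects in every site-by-arm cell of the disease group. Otherwise use the unstratified analysis.
5. Keep the unstratified Fisher result as a sensitivity analysis, and label the adjusted odds ratio as conditional on site.

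Subjects enrolled before version 7 all belong to the icddr,b stratum.

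**Cost.** SAP wording and a table footnote, though the primary estimator and test do change. No new data are needed.
- With no site effect the interval half-width grows by 0.3 points and power falls by 0.5. Corrected CMH loses about 0.7 points at 34 per arm with complete data.
- The t reference matters. With a normal critical value the null rejection rate is 4.9-6.1% (complete data). With t it is 4.5-5.3% with complete data and 4.8-5.2% after imputation.
- The fallback is cheap. At 30 per arm and a 30-point gap, reverting to unstratified loses 0.2-0.3 points of power with 2-3 per arm at the smaller site, and 0.8 with 4.
- The site-conditional log odds ratio is larger, as is its standard error: at a 20-point gap, 1.69 (SE 0.56) becomes 1.79 (SE 0.59), and z moves only from 3.01 to 3.04. Hence the separate label.
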